2.2 Study Rationale

Yoga and mindfulness-based intervention approaches are promising candidates for supporting recovery for women with OUD. There is growing evidence for the positive impact of these contemplative practices for pregnancy, trauma, mental health, pain, and substance use disorders.

Yoga and pregnancy. Yoga interventions may differ in specific orientation, but most are organized around three core components: 1) gentle movement, poses, and stretches to support balance, flexibility and body awareness, 2) focus on breathing, and 3) using breath and sensations within the body to anchor attention to the present moment. Recent reviews of yoga interventions with pregnant women indicate consistent improvements in psychological domains during pregnancy and labor (e.g., depression, anxiety, perceived stress, quality of life and self-efficacy), in physical and pain measures during pregnancy and labor (e.g., discomfort and pain), and in birth variables (e.g., birth weight and number of preterm births). In one randomized controlled study, a single session of yoga reduced state anxiety and cortisol level in depressed pregnant women, and this reduction was maintained throughout the intervention. In another study, women who received a daily yoga and relaxation protocol experienced significantly greater reductions in perceived stress and improvements in reactivity to stress (i.e., increased heart rate variability) relative to those who did not receive the intervention. The positive effects of yoga on depression can extend into the postpartum period.

Yoga and trauma. Emerging evidence supports yoga as an adjunct to care of trauma. Trauma-informed yoga incorporates elements to be sensitive to presenting features of trauma experiences and posttraumatic stress disorder, such as hypervigilance and feelings of not being in control. This approach fosters client choice in all aspects of the practice and sets clear expectations to help clients anticipate what is going to happen from one moment to the next. A randomized controlled trial of a trauma-informed yoga intervention produced greater improvement on PTSD and depression symptom severity relative to a health education class among women with treatment-resistant PTSD. Frequency of yoga practice beyond the study period was associated with greater and prolonged improvements. In another study, participants with PTSD who

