3. STUDY DESIGN

Activities to meet Aim 1. We will evaluate MMORE in a two-group randomized controlled design comparing treatment as usual (TAU) in partner maternity care practices with TAU + MMORE.

Participants will be 150 English-speaking consenting pregnant women aged 18 years and over who have a confirmed singleton pregnancy and are receiving perinatal services and medication for opioid use disorder at partner maternity care practices. We will aim to recruit women in their 2nd/early 3rd trimester of pregnancy.

After completion of the baseline assessment, consented participants will be randomly assigned to participate in the 8-session virtual yoga-mindfulness group intervention or to receive TAU only.

All intervention participants will be provided with a unique password-protected access link to the digital support materials, as well as detailed instructions for how to access the materials. A unique study code will allow us to monitor individual participant use of the support modules for analytic purposes.

All consented participants will complete assessments at baseline, post-intervention (8 weeks for TAU participants) and 3 months postpartum. Participants will complete assessments via a secured, de-identified and password-protected link accessed either on a study-provided laptop computer at a scheduled practice visit or via a protected email link to the user for completion at home or on another secure device with Internet access. Assessments will take approximately 20 minutes to complete. Based on formative data from phase 1 of this project, and other work the research team has conducted with the target population, we anticipate most women will have some access to the Internet either via a mobile phone, tablet, or home computer. If a participant cannot complete an assessment online, a paper version will be provided. The study staff will track ways that participants complete assessments. Participants will receive local gift cards for completion of each assessment.

Activities to meet Aim 2. All study participants (TAU and TAU+MMORE) will complete brief mobile assessments at the end of each week of their assigned cohort period. Assessments will be completed using either a mobile device or computer. Participants will receive a prompt (near end of the week) to complete the assessment. The encrypted, password-protected weekly brief assessment will include items to assess the following:

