- Desire for opioids: A single item, “Did you experience craving for opioids at any point this week?”, anchored on a 10-point scale (0=Not at all; 10=Extremely).
- Mood: Affect will be assessed by representative items from the Positive-Negative Affect Scale (PANAS), adapted to a weekly time orientation.
- Stress will be assessed by a single item “How would you rate your overall level of stress this week?”, anchored on a 7-point scale (No Stress – Worst possible stress)
- Mindfulness. Three mindfulness constructs will be assessed with items from the Awareness (2 items) and Non-Reactivity (2 items) subscales of the Five Factor Mindfulness Questionnaire, and from the Acceptance and Action Questionnaire (2 items).

Activities to meet Aim 3 (Exploratory). A focused implementation evaluation will be conducted with the goal of informing actionable strategies to promote sustainability of MMORE after the NH STR funding has ended. We will use mixed methods to evaluate implementation of MMORE and will draw from implementation science frameworks to guide evaluation. We will use implementation metrics as well as surveys and interviews with participants and obstetric practice stakeholders to evaluate implementation.

At the end of each virtual 8-session intervention period, MMORE participants will complete a Satisfaction Survey regarding their experience (1 to 7 response scale), including: how much liked the intervention, how much the intervention improved awareness of stress and craving triggers, perceived level of confidence to use strategies for awareness, use of acceptance and non-judgment when experienced stress, negative affect and cravings, extent to which intervention helped participant think about their coping strategies and sources of support related to parenting, and likelihood of recommending the intervention to a friend.

We will use the Consolidated Framework for Implementation Research (CFIR) as a conceptual model to guide assessment of barriers and facilitators to implementation and sustainability of MMORE. Interview guides will be constructed with items from the CFIR repository (www.cfir.org) used in other studies. Interviews will tap perspectives related to the intervention itself, attitudes of women with OUD and obstetric and MOUD provider stakeholders about the yoga-mindfulness approaches, and federal and NH state policies (i.e., reimbursement, NH STR initiative) that could support or impede continued offering of the intervention.

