6. STUDY PROCEDURES

6.1 Schedule of Evaluations

Assessment	BL	Intervention	Post	3M PP	Final Evaluation
Eligibility: Consent/Enrollment	X				
Demographics	X				
Current physical conditions that could be considered	x				
AE					
Opioid Abstinence	X		X	X	
MOUD Treatment Retention	X		X	X	
Depression	X		X	X	
Anxiety	X		X	X	
Stress	X		X	X	
Mindfulness	X		X	X	
Pain Perception	X		X	X	
Quality of life	X		X	X	
Substance use (past 3 months, past 30 days)	X		X	X	
Weekly Assessments (craving, mood, stress, mindfulness)		X			
Adverse Events		X	X	X	
Experiences of Care (qualitative)				X	
Fidelity, Acceptability, Reach, Feasibility, Sustainability (Practice Level)					X
Organization Readiness for Implementing Change (Practice Level)		X			X
Program Sustainability (Practice Level)					X

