MOUD Treatment Retention. Treatment retention will be operationalized as a composite of medication adherence (number of weeks buprenorphine or methadone present in the urine toxicology report) and treatment adherence (number of weeks attended required counseling as part of comprehensive treatment as usual, as indicated in clinical notes) - throughout the prenatal period to 3 months postpartum.

Opioid use abstinence. Weekly point of care urine toxicology screening is conducted as part of standard care with all MOUD patients at partner practices to assess for THC, cocaine, benzodiazepines, methamphetamine, opioids, methadone and buprenorphine. Opioid abstinence will be measured as number of weeks consistently abstinent from opioids over the perinatal period to 3 months postpartum.

Secondary End Points:

Other substance use. Other substance use will be measured as number of weeks the participant used marijuana and/or other drugs as indicated in urine toxicology reports. Tobacco and alcohol use will be measured by way of documentation in clinical notes from visits.

Participant Self-Report Procedures: Participants will complete secured online survey assessments at baseline, post-intervention, and 3-months postpartum. The project coordinator will ensure that participants receive the assessment surveys at the specified times in the manner preferred by the participant. If participants wish to receive the survey via email, the survey will be sent as a unique study-identified password-protected link. The project coordinator will monitor and track survey assessment completion and ensure that participants receive gift card incentives for survey completion in a timely manner. For participants who do not wish to complete the survey online, the project coordinator will arrange for either a phone interview with the participant to complete the survey or will mail the participant the survey along with a self-addressed and stamped envelope for the participant to return the survey. The assessment survey will include the following:

Primary End Points:

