Aim 2: For examining mediation/mechanistic effects at the individual-level from longitudinal data via parallel process growth models (paths from treatment assignment to individual-level slope of mediator to individual-level slope of outcome), with 120 individuals, there will be 80% power to detect indirect effects comprised of a small-medium effects of the intervention arm on latent slope of mindfulness (defined as a correlation of 0.25 between variables or equivalently as explaining 6% of the variance in the latent mindfulness slope) and a medium effect of the slope of mindfulness on the slope of the outcome (defined as a correlation of 0.36 or equivalently as explaining 13% of the variance of the outcome). For examining mediation/mechanistic effects at the weekly level, power is less clear. Although DSEM combines aspects of more familiar modeling techniques, it is new and thus limited information is available on determining power for such models. In one set of simulation studies, good model performance was observed for several models differing in complexity for a sample size of 200 individuals with a number of observations per individual ranging from 20-200, and good model performance for all but the most complex models for smaller sample sizes. Thus, with data from 120 individuals contributing up to 8 observations each, we expect to have enough data to accomplish the aim of understanding the mechanisms underlying the intervention effects of MMORE. We will conduct weekly assessments to minimize participant burden. This strategy will still allow us adequate sampling frequency to track changes in outcome measures over the course of treatment. The power

calculations for the mechanistic effects were based on individual-level latent slope variable estimates and are thus not affected by a change to the number of indicator variables for the latent slope variables (reduced from 70 daily assessments to 8 weekly assessments). Power calculations for the dynamic SEM models are approximate and were not specifically based on having daily assessments per individual so will also not change.

Aim 3 is exploratory and not powered.

Treatment Assignment Procedures

Randomization will be conducted via permuted blocks. Once 8-10 participants have enrolled, an intervention will commence for that cohort. The randomization block size would be random, with blocks of size 4, 6, and 8. We plan ongoing recruitment and to start a new group approximately every 8 weeks.

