9.6 Data Analyses

Aim 1

Primary analysis: The difference between treatment arms with respect to likelihood of opioid abstinence and remaining in treatment will be evaluated by logistic generalized estimating equations (GEE). Since these binary outcomes will be evaluated at the 8-week as well as the 3-month postpartum time points, these GEE models will account for the non-independence of repeated measurements within individual. An indicator of treatment arm, time point, as well as an interaction between treatment and time point will be included as predictors in the model along with baseline covariates. Significant differences between the arms will be tested via contrasts involving the treatment*time point interaction term that compare the outcomes at each time point.

The impact of *MMORE* on treatment retention (number of weeks retained) will be evaluated via two-sample t-test if the distribution appears symmetric, but a non-parametric Wilcoxon rank sum test will be used otherwise.

Aim 2

Primary analysis: Analyses of mechanisms of effect of *MMORE* will be performed via parallel process growth models fit via structural equation models, and mediated effects between treatment assignment and outcome will be examined for the following mediator-outcome pairs: craving-abstinence, mindfulness-craving, mindfulness-treatment retention, depression-treatment retention, anxiety-treatment retention, stress-treatment retention, and mindfulness-pain. Since each mediator and outcome variable will be collected at multiple time points, latent intercept and slope effects can be estimated (as in latent growth curves). The parallel process growth models then examine mediation of the effect of an individual-level variable (treatment assignment) on the latent slope of the outcome variable by the latent slope of the mediator variable. For each mediator-outcome pair, a parallel process growth curve model will be fit including both the direct effect of treatment assignment to *MMORE* on the latent slope of the outcome, as well as the indirect effect of *MMORE* on slope of the outcome through the slope of the mediator. Estimates of path coefficients for each individual path as well as of the indirect effect along with a 95% bootstrap confidence interval will be obtained.

To examine these associations we will implement a newly developed modeling strategy called dynamic structural equation models (DSEM). DSEM like non-dynamic SEM are a modeling

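### Craving has no scheduled baseline in either arm, and Aim 2 models built on the weekly items lack a same-scale pre-treatment value

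*Combined protocol and SAP*

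**What the plan says.** Section 3 (activities for Aim 2) sets the timing: "All study participants (TAU and TAU+MMORE) will complete brief mobile assessments at the end of each week of their assigned cohort period". The craving question is a single item, "Did you experience craving for opioids at any point this week". The weekly form also carries PANAS items, one stress item, and mindfulness items from the FFMQ and the Acceptance and Action Questionnaire (AAQ).

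In the section 6.1 schedule, the row "Weekly Assessments (craving, mood, stress, mindfulness" has a mark under Intervention and none under BL, Post or 3M PP.

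The longer surveys are separate. Section 6.2 states: "Participants will complete secured online survey assessments at baseline, post-intervention, and 3-months postpartum". The first of these precedes allocation: "After completion of the baseline assessment, consented participants will be randomly assigned". Sections 6.2 and 9.5.2 list the Edinburgh scales, GAD-7, Perceived Stress Scale and MAAS for these surveys, and section 9.5.2 adds the AAQ. Neither section lists a craving measure.

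Section 9.6 fits parallel process growth models to seven mediator–outcome pairs, beginning "craving-abstinence, mindfulness-craving, mindfulness-treatment retention", and tests mediation from arm to mediator slope to outcome slope. It does not say which instrument supplies each series. Section 9.2 describes the indicators of the latent slopes as "reduced from 70 daily assessments to 8 weekly assessments".

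**The concern.** The first weekly value is taken when the first cohort week is over. A model fitted to weeks 1–8 therefore treats whatever happened between randomisation and the end of week 1 as starting level.

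Two consequences follow for craving, and for any series built on the weekly items:

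- An early arm difference sits in the latent intercept, outside the slope-to-slope indirect effect. With no pre-treatment value, it cannot be distinguished from chance imbalance between the arms.
- Randomisation protects the path from arm to mediator. It does not protect the path from mediator to outcome, where baseline craving is an obvious adjustment variable and is not available.

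Craving matters to two of the seven pairs: it is the mediator in one and the outcome in another. Once a woman has started her cohort, the missing value cannot be recovered.

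**Working it through.** **1. The plan's own Aim 2 figure.** Section 9.2 gives 80% power with 120 women, a correlation of 0.25 for arm to mindfulness slope, and 0.36 for mindfulness slope to outcome slope. The approximate power of each path is Φ(atanh(r)·√(N−3) − 1.96):

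- r = 0.25: Φ(0.2554 × 10.817 − 1.96) = 0.789
- r = 0.36: Φ(0.3769 × 10.817 − 1.96) = 0.983
- Both paths significant: 0.789 × 0.983 = 0.775

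Simulation (60 per arm, no direct effect assumed, 3,000 replicates, 600 bootstrap draws) gives 78.2% with a percentile bootstrap and 83.5% with a bias-corrected one. The stated 80% lies between them, so it is reproduced. It takes the correlations with the slopes as given and does not address when the effect arises.

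**2. Which mediators have a baseline.** Inputs are sections 3, 6.1, 6.2, 9.5.2 and 9.6.

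| Mediator | Pairs as mediator | Baseline survey measure | Weekly measure |
|---|---|---|---|
| Craving | 1 | none listed | single item |
| Mindfulness | 3 | MAAS; probably AAQ | FFMQ and AAQ items |
| Depression | 1 | Edinburgh scales | none |
| Anxiety | 1 | GAD-7 | none |
| Stress | 1 | Perceived Stress Scale | single item |

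So 4 of 5 mediators, covering 6 of 7 pairs, have some pre-randomisation measure. If the stress and mindfulness slopes come from the weekly items, as section 9.2 suggests, only depression and anxiety have a same-scale baseline: 2 of 5 mediators and 2 of 7 pairs. The AAQ items are a possible partial exception.

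**3. What the slope misses.** Assumptions: eight assessments one week apart; baseline at week 0; an arm effect of 0 at baseline, a share f of the week-8 effect at week 1, then a linear rise to 1 at week 8.

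- Weeks 1–8: slope = (1 − f)/7
- Weeks 0–8: slope = Σ(t − 4)y / Σ(t − 4)² = (8 − 4f)/60

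| f | Slope, weeks 1–8 | Slope, weeks 0–8 | Ratio |
|---|---|---|---|
| 0 (delayed) | 0.143 | 0.133 | 107% |
| 1/8 (linear) | 0.125 | 0.125 | 100% |
| 0.5 | 0.0714 | 0.100 | 71% |
| 0.75 | 0.0357 | 0.0833 | 43% |

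If the effect instead builds smoothly with a half-life of 4, 2 or 1 weeks, the ratio is 91%, 80% or 60%.

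**4. Precision.** The sum of squared time deviations is 42 for weeks 1–8 and 60 for weeks 0–8. On that spacing, the error variance of each woman's slope would fall by 1 − 42/60 = 30%. This concerns measurement error in the slope, not true variation between women.

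**The case against.** A reader might infer that the mediation models have no pre-treatment value for any of their mediators. The documents do not support that. Depression, anxiety, stress and mindfulness are all marked at BL in section 6.1. Depression and anxiety are not in the weekly set, so their models must use the survey series. Section 9.5.2 lists acceptance (AAQ) as a secondary outcome, and section 10.1 says secondary outcomes are collected by survey. Section 6.2 does not list the AAQ, which is why its baseline is only probable.

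A reader might also infer that the indirect effect is necessarily understated. It is not: a linear effect gives no bias, and a delayed one reverses the direction. It is tempting to cite section 2.2 ("a single session of yoga reduced state anxiety and cortisol level in depressed pregnant women, and this reduction was maintained throughout the intervention") as evidence of an early effect, but that result concerns state anxiety and cortisol, not craving or mindfulness. The front-loaded shapes are therefore assumptions.

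Three further points can be made for the plan:

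- The growth models estimate intercepts, so an early arm difference is visible. That is true, but it cannot be separated from chance imbalance and does not enter the slope-to-slope effect.
- The survey's items on opioid use disorder severity might touch on craving. They are not listed individually, and any such item would still differ from the weekly question.
- Baseline is completed at consent, while cohorts wait for 8–10 women and start about every 8 weeks (sections 6.2.2 and 9.2). The protocol expects little differential lag, but nothing places baseline one week before the first weekly form. This stands: it limits the figures in steps 3 and 4 and governs how a baseline value should be used.

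**Conclusion.** The point holds in a limited form. Craving has no scheduled baseline in either arm, and any growth model or DSEM resting on the weekly stress, PANAS or FFMQ items lacks a same-scale pre-treatment value. Section 9.6 leaves open which instrument feeds the stress and mindfulness models.

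The size depends on a trajectory that the documents do not give. Over the shapes tried, the week 1–8 slope runs from 43% to 107% of the baseline-inclusive slope, with no bias when the effect is linear. These ratios assume a baseline exactly one week before the first weekly form. No loss of Aim 2 power has been derived.

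The inability to adjust the mediator-to-outcome path for baseline craving does not depend on any assumed shape. This affects the mechanism aim only; the Aim 1 comparisons are untouched. The change is worth making because it is cheap and the value cannot be obtained later.

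**What to change.** Add the weekly craving item, and the weekly stress, PANAS and FFMQ/AAQ items, to the pre-randomisation baseline survey for both arms, and mark them under BL in section 6.1.

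In section 9.6:

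- use the baseline value as a covariate, or as a time point at its actual date in the growth models;
- do not enter it as an equally spaced week 0 in the lag-1 DSEM;
- state which instrument supplies the mediator and the outcome in each of the seven pairs.

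The cost is about 1–2 minutes in a survey that every participant already completes. Women already enrolled will lack the value and must be handled as missing. Repeating the craving item at post-intervention and 3 months postpartum is optional.

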4. SELECTION AND ENROLLMENT OF PARTICIPANTS

4.1 Inclusion Criteria

Eligible participants will be women, 18 years of age or older, English-speaking, carrying a singleton pregnancy, and receiving medication for OUD treatment as part of prenatal care at a partner maternity care practice.

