5. STUDY INTERVENTIONS

5.1 Interventions, Administration, and Duration

Mindful Moms: Yoga Mindfulness Intervention. The significant restrictions to in-person delivery of services at practice partner settings and continued institutional barriers to in-person research at partner settings due to the ongoing Covid pandemic have necessitated the need for alternative safe intervention delivery strategies for the Mindful Moms intervention. After consultation with our partner practice stakeholders and women with lived experience from our study advisory committee, we are modifying the intervention delivery mode to include virtual delivery of the intervention. We will deliver the group intervention virtually through a secured

Dartmouth-based video conferencing software (Zoom). The virtual intervention protocol will be 8 sessions, approximately 60-minutes in duration, conducted over the course of 10 weeks. Lead Instructor [name], professionally trained and certified in prenatal and trauma-informed yoga, will implement the group protocol sessions at the designated location. Sessions will be attended by at least one study team member. Sessions will be video or audio recorded (participants de-identified) to allow for assessment of fidelity in delivery of protocol.

All intervention participants will be provided with a tablet and mobile hotspot if needed in order to be able to access the virtual intervention sessions. All intervention participants will complete a training with research study staff about how to use the videoconferencing software. All intervention participants will be provided with a unique password-protected access link to the online support materials, as well as detailed instructions for how to access the materials. A unique study code will allow us to monitor individual participant use of the support modules for analytic purposes.

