6.2.2 Enrollment, Baseline, and/or Randomization

Enrollment

In this study, the enrollment date will be the date that all of the screening criteria were met, and the individual consents to participate.

Baseline Assessments

Participants will complete the baseline assessment upon consenting to participate in the study. The project coordinators will administer the baseline assessment to the participant through a secure online survey. For participants who do not wish to complete the survey online, the project coordinator will arrange for either a phone interview with the participant to complete the survey or will mail the participant the survey along with a self-addressed and stamped envelope for the participant to return the survey. Both forms of the assessment will be coded with a unique study ID.

Randomization

Following baseline completion, participants will be randomized to condition by the lead project coordinator. The lead project coordinator will meet via phone with participants assigned to the MMORE condition to explain the condition. Participants in the MMORE condition will receive a secure password-protected access to the digital companion features.

Randomization will be conducted via permuted blocks. Once 8-10 participants have enrolled, an intervention will commence for that cohort. The randomization block size would be random, with blocks of size 4, 6, and 8. In thinking about how best to implement our group randomization plan in the context of the reality of recruitment of this high-risk target population, we have developed a plan of ongoing recruitment and starting a new group at least every 8 weeks. With a conservative recruitment

rate of 12 participants per month, we do not anticipate a good deal of differential lag-time between recruitment into the study, completion of baseline, randomization, and start of a new group.

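### No gestational-age limit at entry, and randomisation before the wait for a group: a material share of women may deliver before the 10-week course ends

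*Combined protocol and SAP*

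**What the plan says.** **Who may enter.** Section 4.1: "Eligible participants will be women, 18 years of age or older, English-speaking, carrying a singleton pregnancy, and receiving medication for OUD treatment". It requires that treatment be part of prenatal care at a partner practice, but gives no gestational week. The exclusions in section 4.2 add none. Section 3 states an intention, also without weeks: "We will aim to recruit women in their 2nd/early 3rd trimester of pregnancy".

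**When randomisation happens.** Section 6.2.2: "Following baseline completion, participants will be randomized to condition by the lead project coordinator". Section 4.3 gives the same order. Neither ties allocation to the start of a group.

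**The wait.** Section 6.2.2: "Once 8-10 participants have enrolled, an intervention will commence for that cohort", with "starting a new group at least every 8 weeks". Section 9.2 repeats the plan with an approximate 8-week interval. The protocol's own view of the lag, at a recruitment "rate of 12 participants per month, we do not anticipate a good deal of differential lag-time", is that it will be small.

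**The course and the time points.** Section 5.1 describes eight sessions "conducted over the course of 10 weeks". Section 3 places the Post assessment at the end of the intervention (8 weeks for TAU) and the last one at 3 months postpartum. The primary model in section 9.6 compares the arms at each of these two points.

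**Who is analysed.** Section 9.3 defines the intent-to-treat set as everyone who completes baseline.

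No section says what happens to sessions or to Post if delivery comes first. Section 8 does not list delivery as a reason to stop.

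**The concern.** The time from randomisation to the end of the course is the wait plus 10 weeks. The plan never sets this against the weeks left to delivery. Its remark on lag concerns only the gap between recruitment and group start.

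Two things are at stake. First, births and drop-outs during the wait fall after allocation, so these women stay in the MMORE arm although they had few or no sessions in pregnancy. If that weakens the effect, power falls. Second, Post will find some women still pregnant and others postpartum. Section 2.1 cites discontinuation of 0-33% prenatally against 26-64% postnatally, so one Post estimate would average over very different risks.

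**Working it through.** **1. The plan's own power figure.** Section 9.2 gives 80% power for retention of 60% against 79.2% over 3 time points with within-person correlation 0.5. It recruits 150 with 20% attrition, so 120 are analysed, 60 per arm. I take two-sided 0.05, which section 9.2 states for weeks abstinent.

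- Effective n per arm = 60 × 3 / (1 + 2 × 0.5) = 90.
- Pooled proportion = (0.60 + 0.792)/2 = 0.696.
- Power = Φ[(0.192√90 − 1.96√(2 × 0.696 × 0.304)) / √(0.60 × 0.40 + 0.792 × 0.208)] = Φ[(1.8215 − 1.2750)/0.6362] = Φ(0.859) = 0.805.

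The stated figure reproduces. The plan gives no figure for delivery before the end of the course.

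**2. The wait.** At 12 per month (4.35 weeks per month), 8-10 women take 8/12 × 4.35 = 2.9 to 10/12 × 4.35 = 3.6 weeks. The text does not say whether 8-10 counts both arms. If it counts MMORE women only, 16-20 must be randomised, which takes 5.8-7.2 weeks. Section 6.2.2 caps the interval at 8 weeks. These are the longest waits in a cohort; the last woman to enrol waits hardly at all.

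**3. Latest entry that finishes before delivery at week D** = D − 10 − wait.

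| Delivery | No wait | 3.6 weeks | 8 weeks |
|---|---|---|---|
| 40 weeks | 30 | 26.4 | 22 |
| 37 weeks | 27 | 23.4 | 19 |

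If the eight sessions took 8 weeks instead of 10, each limit would rise by 2 weeks. The 10-week course in section 5.1 and the 8-week Post label in sections 3 and 9.6 should be reconciled in any case.

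**4. Share delivering before the course ends.** The documents give no distribution of entry or delivery. Assumed here: entry uniform over the range shown, wait uniform from 0 to the maximum shown, delivery normal with mean 39 and SD 2 weeks. A woman is counted if entry + wait + 10 > delivery.

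| Entry (weeks) | No wait | Up to 3.6 | Up to 7.2 | Up to 8 |
|---|---|---|---|---|
| 14-28 | 3% | 10% | 21% | 23% |
| 14-30 | 9% | 18% | 29% | 32% |
| 20-30 | 14% | 29% | 46% | 50% |
| 14-36 (allowed by 4.1) | 32% | 40% | 48% | 50% |

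With 150/2 = 75 women in the MMORE arm, 10-30% is about 8 to 22 women. Delivery before the first session is much rarer: at most 0.5% in the first three rows and 8% in the last.

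**5. Post against the 3-month visit.** Taking 3 months as 13 weeks, Post falls on or after that visit if entry ≥ D + 13 − 10 − wait. With the full 8-week wait this is 35 weeks for birth at 40, or 32 weeks for birth at 37. Example: 36 + 8 + 10 = 54, against 40 + 13 = 53. The simulated share is at most about 0.1% for entry up to 32 weeks and at most 2.2% for entry at 14-36 weeks.

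**6. Illustration of dilution.** Take the 18% case.

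- If those women got half the effect, MMORE retention is 60 + 19.2 × (1 − 0.18 × 0.5) = 77.5% and power is 72%.
- If they got none, it is 60 + 19.2 × 0.82 = 75.7% and power is 62%.
- If sessions after birth work equally well, power stays at 80%.

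**The case against.** The best defence has four parts.

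- **Section 3 states a window, and section 6.2.2 foresees a short lag.** Both are true. At the planned recruitment rate with both arms counted, the longest wait is about 3.6 weeks, not 8. This lowers the estimate, but entry after about 26 weeks with that wait still overruns birth at 40 weeks.
- **Nothing says that sessions end at birth.** They are virtual, devices are provided, and the aims speak of pregnant and parenting women. Section 2.1 puts the steepest drop-off between 6 weeks and 3 months postpartum, so later sessions might even help. This stands: dilution is a possibility, and step 6 only illustrates it.
- **Randomisation balances gestational age in expectation,** and TAU women also have an assigned cohort period. This stands too. A reader might infer bias between the arms, but the mixture at Post affects what the estimate means and does not invalidate the comparison.
- **The delivery date is needed for the 3-month visit,** so delivery status at Post can be derived without new data.

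Three further inferences go too far. That many women will deliver mid-course cannot be derived, because the documents give no entry or delivery distribution. The shares are not lower bounds: section 4.1 admits women before 14 weeks as well as after 30. With wait 0-8 weeks and birth at 40, entry at 8-30 weeks gives 4/22 = 18%, against 4/16 = 25% for entry at 14-30. And Post falling after the 3-month visit is an edge case, essentially outside the section 3 aim although section 4.1 allows it.

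**Conclusion.** The concern holds in a limited form. The criteria contain no gestational-age limit, allocation precedes a wait and a 10-week course, and no section deals with delivery in between. A plausible 10-30% of women would deliver before the course ends, with a range of about 3-50% set by the assumed entry ages, waits and delivery dates. The entry limits of 30, 26 and 22 weeks need only the course length, the wait and birth at 40 weeks. The consequences are possible dilution of the effect, avoidable losses after randomisation, and a Post time point that is hard to interpret. This should be changed, but it does not make the trial invalid.

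**What to change.** 1. Amend sections 6.2.2 and 4.3 so that consent and baseline run on a rolling basis, but randomisation takes place only when the cohort's start date is fixed, shortly before session 1, with the same blocks of 4, 6 and 8. Bring section 9.2 into line. Amend section 9.3 so that the intent-to-treat set is all randomised women, since some baseline completers will no longer be randomised.
2. Reconcile section 4.1 with section 3 by making the recruitment window an explicit criterion, in weeks chosen by the sponsor. State whether it is read at consent or at randomisation. Item 1 alone moves losses during the wait ahead of allocation but does not prevent births during the course. If the window is read at randomisation, the wait no longer adds to it (9% instead of 18-32% for a 14-30 week window, under the assumptions above).
3. Derive delivery status at Post from the delivery date and report it by arm.

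A rule that the course must end before the due date is not proposed: it would exclude women inside the intended window, and its effect on recruiting 150 has not been assessed.

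Cost: a protocol amendment, with no new staff or procedures. Some late-presenting women become ineligible, and a few consented women leave before randomisation.
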